8.2.6. Safety Monitoring

8.2.6.1. Hypersensitivity Reactions

Many drugs, but particularly biologic agents, carry the risk of systemic hypersensitivity reactions. If such a reaction occurs, additional data describing each symptom should be provided to the sponsor in the eCRF.

Sites should have appropriately trained medical staff and appropriate medical equipment available when study participants are receiving study drug. It is recommended that participants who experience a systemic hypersensitivity reaction be treated per the local standard of care.

In the case of generalized urticaria or anaphylaxis, additional blood and urine samples should be collected as described in Appendix 2 (Section 10.2). Laboratory results are provided to the sponsor via the central laboratory.

8.2.6.2. Hepatic Monitoring

If a participant develops symptoms that warrant liver function assessment, liver function tests as detailed in Appendix 5 (Section 10.5) should be performed. If these tests are abnormal, clinical and laboratory monitoring should be initiated by the investigator.

Laboratory tests including ALT, AST, alkaline phosphatase (ALP), TBL, direct bilirubin, gamma-glutamyl transferase, and creatine kinase, should be repeated within 48 to 72 hours to confirm the abnormality and to determine if it is increasing or decreasing, if 1 or more of these conditions occur.

8.3. Adverse Events and Serious Adverse Events

Adverse events will be reported by the participant (or, when appropriate, by a caregiver, surrogate, or the participant's legally authorized representative).

The investigator and any qualified designees are responsible for detecting, documenting, and recording events that meet the definition of an AE or SAE and remain responsible for following up AEs that are serious, considered related to the study intervention, study device, or study procedures, or that caused the participant to discontinue the study (see Section 7).

8.3.1. Time Period and Frequency for Collecting AE and SAE Information

All AEs occurring after signing the ICF are recorded in the AE eCRF and assessed for serious criteria.

The SAE reporting to sponsor begins after the participant has signed the ICF and has received study drug. However, if an SAE occurs after signing the ICF, but prior to receiving LY900014, it needs to be reported ONLY if it is considered reasonably possibly related to study procedures.

All SAEs will be recorded and reported to the sponsor or designee immediately and under no circumstance should this exceed 24 hours, as indicated in Appendix 3 (Section 10.3). The investigator will submit any updated SAE data to the sponsor within 24 hours of it being available.

Investigators are not obligated to actively seek AEs or SAEs after conclusion of the study participation. However, if the investigator learns of any SAE, including a death, at any time after a participant has been discharged from the study, and he/she considers the event to be reasonably related to the study intervention or study participation, the investigator must promptly notify the sponsor.

8.3.2. Method of Detecting AEs and SAEs

The method of recording, evaluating, and assessing causality of AEs and SAEs and the procedures for completing and transmitting SAE reports are provided in Appendix 3 (Section 10.3).

Care will be taken not to introduce bias when detecting AEs and/or SAEs. Open-ended and nonleading verbal questioning of the participant is the preferred method to inquire about AE occurrences.

8.3.3. Follow-up of AEs and SAEs

After the initial AE/SAE report, the investigator is required to proactively follow each participant at subsequent visits/contacts. All SAEs will be followed until resolution, stabilization, the event is otherwise explained, or the participant is lost to follow-up (as defined in Section 7.3). Further information on follow-up procedures is provided in Appendix 3 (Section 10.3).

8.3.4. Regulatory Reporting Requirements for SAEs

- Prompt notification by the investigator to the sponsor of a SAE is essential so that legal obligations and ethical responsibilities towards the safety of participants and the safety of a study intervention under clinical investigation are met.
- The sponsor has a legal responsibility to notify both the local regulatory authority and other regulatory agencies about the safety of a study intervention under clinical investigation. The sponsor will comply with country-specific regulatory requirements relating to safety reporting to the regulatory authority, Institutional Review Boards (IRBs)/Independent Ethics Committees (IECs), and investigators.
- An investigator who receives an investigator safety report describing a SAE or other specific safety information (for example, summary or listing of SAEs) from the sponsor will review and then file it along with the IB and will notify the IRB/IEC, if appropriate according to local requirements.

8.3.5. Pregnancy

- Pregnancy (maternal or paternal exposure to IP) does not meet the definition of an AE. However, to fulfill regulatory requirements, any pregnancy should be reported following the SAE process to collect data on the outcome for both mother and fetus.
- If a pregnancy is reported, the investigator should inform the sponsor within 24 hours of learning of the pregnancy and should follow the procedures outlined in Appendix 4 (Section 10.4).
- Abnormal pregnancy outcomes (for example, spontaneous abortion, fetal death, stillbirth, congenital anomalies, ectopic pregnancy) are considered SAEs.

8.3.6. Product Complaints

A product complaint is any written, electronic, or oral communication that alleges a deficiency related to the identity, quality, durability, reliability, safety, effectiveness, or performance of a Lilly product after it is released for distribution. When the ability to use the product safely is impacted, the following are also product complaints:

- a. deficiencies in labeling information, and
- b. use errors for device or combination products due to ergonomic design elements of the product

The sponsor collects product complaints on IPs, medical devices, and drug delivery systems used in clinical studies in order to ensure the safety of study participants, monitor quality, and to facilitate process and product improvements. Complaints are also collected on comparators and other clinical trial material supplied, as required.

Participants will be instructed to contact the investigator as soon as possible if he or she has a complaint or problem with the IP or device, so that the situation can be assessed.

Product complaints will be reported by the investigator to the sponsor per instructions provided on the study specific Product Complaint Form.

As required by local regulations, and per instructions on the product complaint form, the investigator will report to the sponsor and to their IRB/IEC any unanticipated adverse device effect or unanticipated problem that resulted in an SAE (UADE), or any device-related product complaint that could have led to an SAE had precautions not been taken.

8.4. Treatment of Overdose

Excess insulin administration may result in hypoglycemia (Section [8.2.5](#)).

8.5. Pharmacokinetics

Pharmacokinetic parameters are not evaluated in this study.

8.6. Pharmacodynamics

Pharmacodynamic parameters are not evaluated in this study.

8.7. Genetics

Genetics are not evaluated in this study.

8.8. Biomarkers

Biomarkers are not evaluated in this study.

8.9. Immunogenicity Assessments

Immunogenicity will not be assessed in this study.

8.10. Health Economics

8.10.1. Insulin Treatment Satisfaction Questionnaire

The ITSQ (Anderson et al. 2004) is a validated instrument containing 22 items that assesses treatment satisfaction for persons with diabetes on insulin. Items are measured on a 7-point Likert-type scale, where lower scores reflect better outcomes. In addition to an overall score, the items that make up the 5 domains of satisfaction are categorized as:

- Inconvenience of Regimen (5 items)
- Lifestyle Flexibility (3 items)

- Hypoglycemic Control (5 items)
- Glycemic Control (3 items)
- Delivery System (6 items)

8.10.2. Study Mealtime Insulin Experience Question

Study participants will be asked to complete a single Study Mealtime Insulin Experience question specifically developed for this study. This is a participant-rated assessment of their likelihood of incorporating the mealtime insulin used in this study (that is, LY900014) in their diabetes management routine. The question is rated on a 5-point scale ranging from “1- Very unlikely” to “5- Very likely.”

8.10.3. Diabetes-Specific Attitudes about Technology Use (DSAT)

The Diabetes-Specific Attitudes about Technology Use scale (DSAT) is a 5-item scale that was originally developed to assess T1D patients’ attitudes towards diabetes-specific technology (Tanenbaum et al. 2017). Each item is rated on a 5-point Likert scale to indicate agreement with the statement, with higher scores indicating more positive attitudes about devices and technology. Individual ratings are summed to obtain a total score.

9. Statistical Considerations

9.1. Statistical Hypotheses

The primary objective of this study is to evaluate the change of time glucose values from CGM are within target range (70-180 mg/dL [3.9-10.0 mmol/L]) during the daytime period from baseline to endpoint at Week 12 with LY900014 treatment.

9.2. Sample Size Determination

Approximately 167 participants will be assigned to treatment with LY900014 such that 150 participants complete the study through the primary endpoint at Week 12. This sample size has approximately 80% power to detect an increase of 4.5% time in target range (70-180 mg/dL [3.9-10.0 mmol/L]) during the daytime period from baseline, assuming no true difference in time in target range between baseline and endpoint, and a standard deviation (SD) of 19.5%.

Assuming a 10% dropout rate for 12 weeks, approximately 167 participants will need to be assigned.

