6.3. Measures to Minimize Bias: Randomization and Blinding

This is an open-label, single arm study.

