9.4. Statistical Analyses

9.4.1. General Considerations

Statistical analysis of this study will be the responsibility of Lilly or its designee. Any change to the data analysis methods described in the protocol will require an amendment ONLY if it changes a principal feature of the protocol. Any other change to the data analysis methods described in the protocol, and the justification for making the change, will be described in the statistical analysis plan (SAP) or the clinical study report (CSR). Additional exploratory analyses of data will be conducted as deemed appropriate.

The SAP will be finalized prior to the first patient first visit and it will include a more technical and detailed description of the statistical analyses described in this section. This section is a summary of the planned statistical analyses of the most important endpoints, including primary and key secondary endpoints. The primary analysis is for the treatment period through Week 12.

To ensure that the CGM outcome variables are only calculated from CGM session days with

sufficient data within the 24-hour and daytime periods, the following criterion will be used to determine a valid CGM session day to be counted into the calculation for a visit:

minimum number of measures per day – at least 70% of the total measures that are supposed to be obtained for the 24-hour period

Efficacy analyses will be conducted on the treated population, including data collected prior to permanent discontinuation of IP. When change from baseline is included as a *response variable of analysis models*, the participant will be included in the analysis only if a baseline and a postbaseline measurement are available.

Safety analyses will be conducted on the treated population. Analyses of AEs and severe hypoglycemia will include data collected during the treatment period (Visit 4-12). AEs during the follow-up period will be listed. Analyses of AEs for the baseline period may be conducted as needed.

Unless otherwise noted, all tests will be conducted at a 2-sided alpha level of 0.05, and CIs will be calculated at 95%, 2-sided. A gatekeeper method (Westfall and Krishen 2001) will be used to control the overall type 1 error for the primary and gated secondary objectives.

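### Does assuming no true change from baseline undermine the stated 80% power with 150 completers?

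*Protocol*

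**What the plan says.** Protocol 9.2 gives the basis for the sample size, and SAP 5.2 repeats it. The claim is: "This sample size has approximately 80% power to detect an increase of 4.5% time in target range", for the daytime period and measured from baseline. Two conditions follow in the same sentence: "assuming no true difference in time in target range between baseline and endpoint, and a standard deviation (SD) of 19.5" percent. The number of completers is set so that "150 participants complete the study through the primary endpoint at Week 12", and the number assigned follows from the dropout allowance: "Assuming a 10% dropout rate for 12 weeks, approximately 167 participants will need to be assigned".

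The rest of the plan fixes the setting. Protocol 6.3 says "This is an open-label, single arm study". Protocol 9.4.1 says that, unless noted otherwise, "all tests will be conducted at a 2-sided alpha level of 0.05". Protocol 9.1 defines the primary objective as the change from baseline to Week 12, and Protocol 9.4.2 analyses that change with a mixed model for repeated measures (MMRM). Protocol 9.4.3 opens the gate to the secondary objectives only if the primary comparison of endpoint with baseline is significant at the two-sided 0.05 level. No non-inferiority or equivalence margin is given for this study.

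**The concern.** Power to detect an increase is the probability of rejecting the null when that increase is real. A power statement conditional on no change is therefore self-contradictory: without a true change, the rejection probability is the type I error rate. Protocol 9.1 states an objective but no formal null or alternative, and the SAP carries the same sentence, so neither document corrects the other.

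The unlabelled SD adds to the doubt. A figure of 19.5 could be the SD of the within-participant change, or the SD of time in range at a single visit. In the second case the power depends on the correlation between baseline and Week 12, which the documents do not give. If the intended inputs were not those that yield 80%, the trial could be too small for its primary test.

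**Working it through.** **Inputs.** Completers n = 150, effect 4.5 percentage points, SD 19.5 percentage points, dropout 10% (Protocol 9.2 and SAP 5.2). Two-sided alpha 0.05 (Protocol 9.4.1). Single arm, change from baseline (Protocol 6.3 and 9.4.2). The documents do not name the test behind the calculation; I take a one-sample t-test on the change, the simple counterpart of the planned model.

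**Reproducing the plan's figure.** With 19.5 as the SD of the change:

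- Standardised effect: δ√n / SD = 4.5 × √150 / 19.5 = 4.5 × 12.247 / 19.5 = 2.826.
- Normal approximation: power = Φ(2.826 − 1.960) = Φ(0.866) = 80.7%.
- Noncentral t with 149 degrees of freedom: power = 80.2%.
- Required n, normal approximation: [19.5 × (1.960 + 0.842) / 4.5]² = 147.4, so 148. By the t calculation, the smallest n that reaches 80% is 150, exactly the plan's number.
- Assigned: 150 / (1 − 0.10) = 166.7, so 167, again the plan's number.

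**Taking the clause literally.** With a true change of 0, the same test rejects with probability 5.0%: 2.5% for an increase and 2.5% for a decrease. This is alpha. It would be 5.0% at any sample size, so it says nothing about whether 150 is enough.

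**Other readings of the sentence, all at n = 150 in total unless noted.**

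| Reading | Power |
|---|---|
| One-sample t, two-sided 0.05, true change 4.5 | 80.2% |
| Same, one-sided 0.05 | 87.9% |
| Two independent groups, 75 per group | 29.2% |
| Two independent groups, 150 per group | 51.5% |
| Equivalence, margin ±4.5, true change 0, one-sided 0.05 tests | 76.3% |
| Equivalence, margin ±4.5, true change 0, one-sided 0.025 tests | 61.4% |
| One-sample non-inferiority, margin 4.5, true change 0, one-sided 0.025 | 80.2% |

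The last row equals the first, apart from the negligible lower tail, because moving the margin by 4.5 is the same calculation as moving the true mean by 4.5. It offers a plausible origin for the clause, as leftover non-inferiority wording, but it is not the planned test.

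**The SD.** If 19.5 were a single-visit SD, equal at both visits, the SD of the change would be 19.5 × √[2(1 − ρ)]. The correlations below are assumptions.

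| ρ | SD of change | Power |
|---|---|---|
| 0 | 27.6 | 51.0% |
| 0.25 | 23.9 | 63.0% |
| 0.5 | 19.5 | 80.2% |
| 0.75 | 13.8 | 97.8% |

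The single-visit reading gives the plan's 80% only at ρ = 0.5, where the SD of the change is itself 19.5. Either route to the stated power leads to the same SD of change.

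**The case for a change.** The best case for editing is that a sample-size statement should let a reader reproduce the number from what is written. Here the reader must set aside one stated condition and infer the meaning of another. The clause cannot be excused as a statement of the null, because it is listed beside the SD as a condition for the power. A non-inferiority reading does not rescue it either, since no margin is given and the gate is a two-sided test against baseline. The sentence could also be carried unchanged into the study report.

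Much of this stands. The clause is in the current text of both documents, it conflicts with the effect in its own sentence, and no other section corrects it. An explicit label on the SD would be clearer.

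The further step, that the stated power is unsupported, does not follow. A claim of power to detect a given increase is the ordinary way to state the alternative, so the effect size is on the page, and the clause conflicts with it without erasing it. The sentence concerns an increase from baseline in a single-arm study whose primary endpoint is change, so reading 19.5 as the SD of that change is natural, and it reproduces the smallest n for 80% exactly. The 5% figure is the type I error rate and should not be presented as the power of the design.

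**Conclusion.** The wording is inconsistent; the calculation is not. For a two-sided 0.05 test of change from baseline, with a true mean increase of 4.5 points and an SD of change of 19.5 points, 150 completers give 80.2% power, and a 10% dropout allowance gives 167 assigned. These are the plan's own numbers.

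The slip is clerical. Dropping the clause and labelling the SD would leave enrolment, alpha, the primary model and the testing sequence where they are, and would alter no conclusion of the trial. A statistician checking the figure will reach the intended inputs from the sentence and the design.

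This rests on two assumptions: that the calculation used a one-sample test on the change, and that 19.5 is the SD of that change. The exact match at n = 150 supports both, although the documents state neither. The check confirms the arithmetic; it does not show that 19.5 will prove the right SD in this population, which is a separate matter. No change to the plan follows.

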9.3. Populations for Analyses

The following populations are defined:

Population	Description
Entered	All participants who give informed consent
Enrolled	All participants who continue the study after Visit 2.
Treated	All enrolled participants who receive at least 1 dose of the assigned IP after Visit 4

Abbreviations: IP = investigational product.

9.4. Statistical Analyses

9.4.1. General Considerations

Statistical analysis of this study will be the responsibility of Lilly or its designee. Any change to the data analysis methods described in the protocol will require an amendment ONLY if it changes a principal feature of the protocol. Any other change to the data analysis methods described in the protocol, and the justification for making the change, will be described in the statistical analysis plan (SAP) or the clinical study report (CSR). Additional exploratory analyses of data will be conducted as deemed appropriate.

The SAP will be finalized prior to the first patient first visit and it will include a more technical and detailed description of the statistical analyses described in this section. This section is a summary of the planned statistical analyses of the most important endpoints, including primary and key secondary endpoints. The primary analysis is for the treatment period through Week 12.

To ensure that the CGM outcome variables are only calculated from CGM session days with

sufficient data within the 24-hour and daytime periods, the following criterion will be used to determine a valid CGM session day to be counted into the calculation for a visit:

minimum number of measures per day – at least 70% of the total measures that are supposed to be obtained for the 24-hour period

Efficacy analyses will be conducted on the treated population, including data collected prior to permanent discontinuation of IP. When change from baseline is included as a *response variable of analysis models*, the participant will be included in the analysis only if a baseline and a postbaseline measurement are available.

Safety analyses will be conducted on the treated population. Analyses of AEs and severe hypoglycemia will include data collected during the treatment period (Visit 4-12). AEs during the follow-up period will be listed. Analyses of AEs for the baseline period may be conducted as needed.

Unless otherwise noted, all tests will be conducted at a 2-sided alpha level of 0.05, and CIs will be calculated at 95%, 2-sided. A gatekeeper method (Westfall and Krishen 2001) will be used to control the overall type 1 error for the primary and gated secondary objectives.

Baseline is defined as the last nonmissing measurement at or before Visit 4 unless otherwise specified. Daytime is defined as 0600 hours to midnight (06:00-23:59 on the 24-hour clock) and nighttime is defined as midnight to 0600 hours (00:00-05:59 on the 24-hour clock).

A restricted-maximum-likelihood-based, mixed model repeated measures (MMRM) analysis will be used to analyze continuous longitudinal variables. All the longitudinal observations at each scheduled postbaseline visit will be included in the analysis. The model for the analysis of the primary efficacy endpoint of change from baseline in time in target range (70-180 mg/dL [3.9-10.0 mmol/L]) during daytime period will include the fixed class effect of visit, the covariate of baseline, and the random effect of participant. An unstructured covariance structure will be used to model the within-participant errors. Significance tests will be based on least-squares means and Type III tests. SAS® PROC MIXED will be used to perform the analysis. If this analysis fails to converge, the following covariance structures will be tested in order:

- Toeplitz with heterogeneity
- autoregressive with heterogeneity
- compound symmetry with heterogeneous variances
- Toeplitz
- autoregressive
- compound symmetry without heterogeneous variances

The first covariance structure that converges will be used. The Kenward-Roger approximation will be used to estimate denominator degrees of freedom.

An analysis of covariance (ANCOVA) will also be used to analyze continuous variables collected only at baseline and endpoint. The model will include baseline as a covariate. Unless

otherwise stated, missing endpoints will be imputed using the last-observation-carried-forward (LOCF) approach, using only postbaseline data.

For continuous measures, summary statistics will include sample size, mean, SD, median, minimum, and maximum for both the actual and the change from baseline measurements. Least-square means and standard errors derived from the analysis models will also be displayed for the change from baseline measurements.

For categorical measures, summary statistics will include sample size, frequency, and percentages.

